7.2.4 Evaluating Adverse Events

An investigator who is a qualified physician will evaluate all adverse events according to the NCI Common Terminology for Adverse Events (CTCAE), version 4.0. Any adverse event which changes CTCAE grade over the course of a given episode will have each change of grade recorded on the adverse event case report forms/worksheets.

All adverse events regardless of CTCAE grade must also be evaluated for seriousness.

Table 10 Evaluating Adverse Events

An investigator who is a qualified physician will evaluate all adverse events as to:

V4.0 CTCAE Grading	Grade 1	Mild; asymptomatic or mild symptoms; clinical or diagnostic observations only; intervention not indicated.
	Grade 2	Moderate; minimal, local or noninvasive intervention indicated; limiting age-appropriate instrumental ADL.
	Grade 3	Severe or medically significant but not immediately life-threatening; hospitalization or prolongation or hospitalization indicated; disabling; limiting self-care ADL.
	Grade 4	Life threatening consequences; urgent intervention indicated.
	Grade 5	Death related to AE
Seriousness	A serious adverse event is any adverse event occurring at any dose or during any use of Merck product that:	
	† Results in death; or	
	† Is life threatening; or places the subject, in the view of the investigator, at immediate risk of death from the event as it occurred (Note: This does not include an adverse event that, had it occurred in a more severe form, might have caused death.); or	
	† Results in a persistent or significant disability/incapacity (substantial disruption of one's ability to conduct normal life functions); or	
	† Results in or prolongs an existing inpatient hospitalization (hospitalization is defined as an inpatient admission, regardless of length of stay, even if the hospitalization is a precautionary measure for continued observation. (Note: Hospitalization [including hospitalization for an elective procedure] for a preexisting condition which has not worsened does not constitute a serious adverse event.); or	
	† Is a congenital anomaly/birth defect (in offspring of subject taking the product regardless of time to diagnosis); or	
	Is a new cancer; (that is not a condition of the study) or	
	Is an overdose (whether accidental or intentional). Any adverse event associated with an overdose is considered a serious adverse event. An overdose that is not associated with an adverse event is considered a non-serious event of clinical interest and must be reported within 24 hours.	
	Other important medical events that may not result in death, not be life threatening, or not require hospitalization may be considered a serious adverse event when, based upon appropriate medical judgment, the event may jeopardize the subject and may require medical or surgical intervention to prevent one of the outcomes listed previously (designated above by a †).	
Duration	Record the start and stop dates of the adverse event. If less than 1 day, indicate the appropriate length of time and units	
Action taken	Did the adverse event cause the Merck product to be discontinued?	
Relationship to test drug	Did the Merck product cause the adverse event? The determination of the likelihood that the Merck product caused the adverse event will be provided by an investigator who is a qualified physician. The investigator's signed/dated initials on the source document or worksheet that supports the causality noted on the AE form, ensures that a medically qualified assessment of causality was done. This initialed document must be retained for the required regulatory time frame. The criteria below are intended as reference guidelines to assist the investigator in assessing the likelihood of a relationship between the test drug and the adverse event based upon the available information. The following components are to be used to assess the relationship between the Merck product and the AE; the greater the correlation with the components and their respective elements (in number and/or intensity), the more likely the Merck product caused the adverse event (AE):	
	Exposure	Is there evidence that the subject was actually exposed to the Merck product such as: reliable history, acceptable compliance assessment (pill count, diary, etc.), expected pharmacologic effect, or measurement of drug/metabolite in bodily specimen?
	Time Course	Did the AE follow in a reasonable temporal sequence from administration of the Merck product? Is the time of onset of the AE compatible with a drug-induced effect (applies to trials with investigational medicinal product)?
	Likely Cause	Is the AE not reasonably explained by another etiology such as underlying disease, other drug(s)/vaccine(s), or other host or environmental factors

Relationship to Merck product (continued)		The following components are to be used to assess the relationship between the test drug and the AE: (continued)	
	Dechallenge	
Was the Merck product discontinued or dose/exposure/frequency reduced? If yes, did the AE resolve or improve? If yes, this is a positive dechallenge. If no, this is a negative dechallenge.
 
(Note: This criterion is not applicable if: (1) the AE resulted in death or permanent disability; (2) the AE resolved/improved despite continuation of the Merck product; or (3) the trial is a single-dose drug trial); or (4) Merck product(s) is/are only used one time.)
	
	Rechallenge	
Was the subject re-exposed to the Merck product in this study? If yes, did the AE recur or worsen? If yes, this is a positive rechallenge. If no, this is a negative rechallenge.
 
(Note: This criterion is not applicable if: (1) the initial AE resulted in death or permanent disability, or (2) the trial is a single-dose drug trial); or (3) Merck product(s) is/are used only one time).
 
NOTE: IF A RECHALLENGE IS PLANNED FOR AN ADVERSE EVENT WHICH WAS SERIOUS AND WHICH MAY HAVE BEEN CAUSED BY THE MERCK PRODUCT, OR IF REEXPOSURE TO THE MERCK PRODUCT POSES ADDITIONAL POTENTIAL SIGNIFICANT RISK TO THE SUBJECT, THEN THE RECHALLENGE MUST BE APPROVED IN ADVANCE BY THE U.S. CLINICAL MONITOR AS PER DOSE MODIFICATION GUIDELINES IN THE PROTOCOL.
	
	Consistency with Trial Treatment Profile	Is the clinical/pathological presentation of the AE consistent with previous knowledge regarding the Merck product or drug class pharmacology or toxicology?	
The assessment of relationship will be reported on the case report forms /worksheets by an investigator who is a qualified physician according to his/her best clinical judgment, including consideration of the above elements.			
Record one of the following		Use the following scale of criteria as guidance (not all criteria must be present to be indicative of a Merck product relationship).	
Yes, there is a reasonable possibility of Merck product relationship.		There is evidence of exposure to the Merck product. The temporal sequence of the AE onset relative to the administration of the Merck product is reasonable. The AE is more likely explained by the Merck product than by another cause.	
No, there is not a reasonable possibility Merck product relationship		Subject did not receive the Merck product OR temporal sequence of the AE onset relative to administration of the Merck product is not reasonable OR there is another obvious cause of the AE. (Also entered for a subject with overdose without an associated AE.)	

7.2.5 Sponsor Responsibility for Reporting Adverse Events

All Adverse Events will be reported to regulatory authorities, IRB/IECs and investigators in accordance with all applicable global laws and regulations.

7.2.6 Adverse Event Collection

Adverse events forms developed by the sponsor institution will be distributed and collected to document adverse events of interest. The sponsor institution will collect, maintain, and monitor CRFs.

8.0 BIOMARKERS AND CORRELATIVE STUDIES

8.1 Biomarker Study Overview

Tumor *GNAQ* and *GNA11* status will be determined for all patients treated on this study using archived or newly acquired tumor material. PD-L1 expression by IHC will also be performed on all baseline tumor samples (either archival or new biopsies). All patients with safely accessible tumor will undergo pre- and post-treatment (day 14 +/- 3 days) tumor biopsies for biomarker and correlative analysis. The decision to not pursue these biopsies must be made in collaboration with the Principal Investigator. An additional tumor biopsy will be requested from patients at the time of disease progression; however, this biopsy is optional.

In addition to *GNAQ* and *GNA11* mutational status and PD-L1 staining, peripheral blood and tumor will be collected to assess other immune correlates including but not limited to peripheral circulating lymphocytes and tumor infiltrating lymphocytes prior to therapy and at the time of progression by multiplexed mass cytometry. Specific populations of T cells assessed will include (but not limited to) CD8+ cytotoxic T cells, regulatory T cells, and PD-1+ T cells.

8.2 Correlative Studies

8.2.1 Tumor Biopsies

Investigators are highly encouraged to collect tumor biopsies at baseline (in the absence of sufficient archival tissue) and 14 days (+/- 3 days) following initiation of therapy, with an optional tumor biopsy conducted at the time of disease progression. The pre-treatment biopsy will be obtained within 28 days of starting therapy. As noted, archival tissue within one year of starting therapy of sufficient quantity will preclude the need for an initial biopsy. Issues that would cause treatment delays should be discussed with the PI who may grant permission on a case-by-case basis to analyze tissue from a protocol pre-treatment biopsy that has occurred greater than 28 days prior to study treatment. The post-treatment biopsy will be performed at day 14 ± 3 days following the morning dose of the study medications. An optional third tumor biopsy will be requested of these patients at the time of tumor progression, with particular efforts made at obtaining such biopsies in patients who have developed progression after achieving a radiographic response to treatment or after prolonged disease control (i.e., greater than 4 months). Up to eight core samples will be obtained with each biopsy, providing sufficient tissue for the correlative studies.

Tissue will be divided such that a portion (one core in the case of core needle biopsy procedures) is formalin fixed and designated for immunohistochemistry (IHC) and the remainder flash frozen in liquid nitrogen.

Fresh tumor biopsy samples should be snap-frozen using liquid nitrogen or a dry ice slurry as outlined [below](#). The tissue must be frozen as soon as possible after biopsy to minimize any form of degradation and to avoid risking the viability of the tissue.

Snap-Freezing in Liquid Nitrogen:

- Label cryogenic vial(s) with the subject's study identification number (ie. Accession number for MSKCC patients), the date of collection, time point (baseline, day 14, or progression) and the study center performing the biopsy. Ensure that the label adheres to the vial and does not come off when placed in liquid nitrogen. Labels cannot be adequately affixed to the vials after freezing.
- Immediately place the freshly obtained tissue into the labelled cryogenic vial. Place the vial with tissue in liquid nitrogen for 2 minutes or longer to snap-freeze the tissue. Tumor cores should be frozen individually in separate cryovials as collected in order to minimize the time between removal and freezing.
- Remove the cryogenic vial from the liquid nitrogen.
- Store the sample in a -80°C freezer (-65°C to -80°C is acceptable) until ready for shipping.

Freezing Procedure with Dry Ice Slurry

- Materials required include: 5 lbs dry ice, alcohol (ethanol or comparable), basin, long forceps
- Place at least 5 lbs of dry ice into a basin and pour one liter of alcohol over the ice.
- Label cryogenic vial(s) with the subject's study identification number, the date of collection, and the study center performing the biopsy. Ensure that the label adheres to the vial and does not come off when placed in liquid nitrogen. Labels cannot be adequately affixed to the vials after freezing.
- Immediately place the freshly obtained tissue into the labelled cryogenic vial. Place the vial with tissue in liquid nitrogen for 2 minutes or longer to snap-freeze the tissue. Tumor cores should be frozen individually in separate cryovials as collected in order to minimize the time between removal and freezing.
- Place the lower half of the sealed cryotube containing tissue into the solution for at least 2 minutes until frozen solid.
- Store the sample in a -80°C freezer (-65°C to -80°C is acceptable) until ready for shipping.

8.2.2 PD-L1 Staining Assay

Archival or fresh tissue biopsies obtained prior to start of treatment will be subjected to PD-L1 by immunohistochemistry per a proprietary assay. Percentage of tumor cells expressing PD-L1 will be correlated to duration of progression-free survival. Cutoffs of strong PD-L1 staining

Product: MK-3475

Protocol/Amendment No. 03

($\geq 50\%$ of cells) and weak PD-L1 staining (1-49% of cells) will be used and correlated with response rate by irRECIST criteria.

Biopsies should be processed in the following manner:

- Formalin fixed paraffin embedded tissue samples are acceptable; a fine needle aspirate, frozen sample, plastic embedded sample, cell block, clot, bone, bone marrow or cytologic specimen will not be acceptable for IHC analysis.
- It is recommended that FFPE blocks be sectioned fresh (within 7 days of sectioning and sending for PD-L1 analysis) onto positively charged slides; slides should be stored and shipped (and stored upon receipt at Qualtek) at 2-8C in the dark.
- Recommended fixation time for samples is 24 hours to 48 hours in 10% neutral buffered formalin.

8.2.3 Blood Collection

Two 10 ml sodium heparin tubes will be collected from patients prior to treatment, at the beginning of cycle 2 (week 3), and at the time of progression. Samples will be subsequently stored for future correlative studies. The samples drawn prior to treatment can be drawn on C1W1 prior to initiation of study drug.

Process samples in the following manner.

- Utilizing the 3 sodium heparin tubes, use your institutions choice of best practices to isolate mononuclear cells (i.e., accuspin system, leucosep system, CPT tubes, general ficoll layering).
- Transfer the cells to a BD Falcon ® tube and wash the cells three times with PBS (ex: aliquot cellular layer to falcon tube and fill with 15 ml of PBS, invert several times to mix. Cap and centrifuge at 300 x g for 10 min, pour off PBS and repeat).
- After the third wash, carefully pour off the PBS one last time and freeze the cell pellet at -80°C until shipment to the respective biorepository
- Label tubes with the subject's study identification number, initials, the date of collection, time point and protocol number.

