4.2.3.2 Biomarker Research

To assess whether common genetic and protein expression characteristics in uveal melanoma correlate with ORR, we will assess *GNAQ/GNA11* mutation status on each patient per institutional protocol. We will furthermore evaluate PD-L1 expression status on archival or fresh tissue from all patients and correlate with ORR.

This study will also investigate other molecular characteristics of uveal melanoma when treated with pembrolizumab. Analysis will focus on tumor and blood markers prior to therapy and early-on-treatment (at the time of the second dose).

Strongly encouraged tumor biopsies may also be performed to allow for assessment of the pharmacodynamics effects of pembrolizumab treatment. Such biopsies may be performed within 21 days of the start of treatment, and on Cycle 2 Day 1 (+/- 3 days). Assessment of these samples will include, but are not limited to, changes in lymphocyte profile in the tumor and blood.

Blood samples (2X 10 ml) will be collected as indicated in the Time and Events Table (see Section 7.1). Blood will be processed to isolate both PBMCs and serum for future biomarker analyses at the conclusion of the study, as to be determined by the investigators based on the

Protocol date: August 30, 2016

Confidential

state of knowledge at that time, and available molecular analysis platforms. Possible analyses include, but are not limited to, immune cell populations, circulating free DNA (cfDNA), circulating miRNA, and proteins/cytokines.

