13 A newly obtained biopsy sample of at least one tumor lesion or acceptable archival tissue prior to therapy start is required in all patients for PD-L1 evaluation. PD-L1 status must be assessed, and if the tumor biopsy submitted is inadequate for determination of PD-L1 status by immunohistochemistry at a central pathology laboratory, a repeat biopsy is encouraged. If a biopsy at baseline is not judged to be safe by the investigator, this requirement will be waived. Additional biopsy samples approximately at Week 3 and at disease progression are highly desirable when it is feasible. The tissue sample should have proper size to enable multiple planned biomarker analyses, and fine needle aspiration will not be acceptable. The biopsy techniques allowed in the study include core needle biopsies or surgical biopsies. Study sites should use the same biopsy techniques in this study as they routinely use for a given tumor lesion/location. Detailed instructions for tissue collection, processing and shipment are provided in section 8.2.1.														
14 Informed consent for future biomedical research samples must be obtained before the DNA sample. DNA sample for analysis should be obtained predose, on Day 1 (or with the next scheduled blood draw), as the last sample drawn, on randomized subjects only, or at a later date as soon as the informed consent is obtained. 20mL in two 10mL sodium heparin tubes will be collected at each time point.														
15 Tumor imaging should be performed at week 18 and week 24 but should be repeated only every 12 weeks thereafter or as clinically indicated.														
16 PLEASE NOTE- This visit is to be completed within 3 weeks of a patient experiencing disease progression, intolerable toxicity or withdrawal of consent. For Imaging Only- If a scan has been performed within 6 weeks of this visit, the site does not need to repeat the scan.														
17 If subjects discontinue therapy for reasons other than disease progression, they should be followed in the clinic every 3 months with surveillance studies as indicated until completion of the study. At the time of subsequent progression, if Second Cycle Treatment is not pursued, then subjects should be followed by phone contact every 3 months														
18 If subjects discontinue therapy for disease progression, they should be followed by for overall survival by phone contact every 3 months until completion of the study														

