Assessment of peripheral blood lymphocyte profiles may also yield critical insights into response and resistance to pembrolizumab. Blood collection is required on day 1 of pembrolizumab treatment, two weeks into treatment (cycle 2), and at the time of progression. Twenty (20) ml of peripheral blood should be obtained at each timepoint.

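### The blood procedure keeps only a washed cell pellet from heparin tubes, so the serum planned in Section 4.2.3.2 is never obtained and no preservation step is stated for cells meant for mass cytometry

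*Combined protocol and SAP*

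**What the plan says.** **What is to be obtained.** Section 4.2.3.2 (Biomarker Research) states as a plan: "Blood will be processed to isolate both PBMCs and serum for future biomarker analyses at the conclusion of the study". The assays are left to the investigators at study end. The possibilities named are "immune cell populations, circulating free DNA (cfDNA), circulating miRNA, and proteins/cytokines".

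**What the cells are for.** Section 8.1 says that blood and tumor will be collected to assess immune correlates, including circulating and tumor-infiltrating lymphocytes, "prior to therapy and at the time of progression by multiplexed mass cytometry". It names CD8+ cytotoxic, regulatory and PD-1+ T cells.

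**What is drawn.** Section 8.2.3: "Two 10 ml sodium heparin tubes will be collected from patients prior to treatment", and again at the start of cycle 2 and at progression. Footnote 14 of the flow chart in Section 6.1 agrees: "20mL in two 10mL sodium heparin tubes will be collected at each time point". Section 7.1.2.6 gives the total: "Twenty (20) ml of peripheral blood should be obtained at each timepoint".

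**What is done with it.** Section 8.2.3 begins the processing with "Utilizing the 3 sodium heparin tubes". Each institution chooses how to isolate mononuclear cells. The remaining steps are prescribed: wash three times in PBS, then "carefully pour off the PBS one last time and freeze the cell pellet at" -80°C until shipment. No step concerns serum, plasma, a freezing medium or a fixative.

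**The concern.** Section 4.2.3.2 postpones the choice of assay to the end of the study. That works only if the right fractions are stored at the time of each draw, because fluid discarded during processing cannot be recovered later. If sites follow Section 8.2.3 to the letter, the fluid-phase options close without anyone deciding to close them.

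The cell fraction raises a related question. Mass cytometry reads single cells, and the text does not say how the cells are kept intact through freezing. Patients give 20 mL at each time point for this purpose, and Section 7.1.2.6 makes the collection a requirement, so the stored material should match the stated use.

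**Working it through.** No error rate, power or event count enters this point. The check sets the sections side by side, with simple volume arithmetic.

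**1. Is there blood left for a serum tube?** Tubes (Section 8.2.3 and footnote 14) × volume = 2 × 10 mL = 20 mL. Total per time point (Section 7.1.2.6) = 20 mL. Remainder = 20 − 20 = 0 mL. Section 4.2.3.2 itself also gives two 10 mL samples. The two flow charts and the laboratory table in Section 7.1.4.1 list correlative blood without a serum tube.

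**2. Can the tubes drawn give serum?** Serum is the fluid left after blood has clotted. Heparin prevents clotting, so these tubes could give plasma at most. Section 8.2.3 has no step that sets plasma aside.

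**3. What is stored, against what is named?**

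| Possible analysis (Section 4.2.3.2) | Fraction needed | Stored under Section 8.2.3 |
|---|---|---|
| Immune cell populations | Cells | Washed pellet, no preservation step stated |
| cfDNA | Serum or plasma | None |
| Circulating miRNA | Serum or plasma | None |
| Proteins/cytokines | Serum or plasma | None |

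**4. Are the cells kept in a form suited to cytometry?** The documents give the assay (Section 8.1) and the freezing step (Section 8.2.3). They do not say that the two are incompatible. General laboratory knowledge supplies that link: the assay needs intact cells, and a pellet frozen without cryoprotectant or fixation largely loses them, though it can still serve for nucleic acid. The latitude given to institutions covers isolation of the cells, not the freezing. Section 8.1 places cytometry before therapy and at progression, which is two of the three first-course time points.

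**5. Tube count.** Three 10 mL tubes would be 3 × 10 = 30 mL, against the 20 mL stated elsewhere. Sections 4.2.3.2 and 7.1.2.6, footnote 14 and the opening of Section 8.2.3 all support two.

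**6. What would a serum tube cost?** Blood left for PBMCs = 20 − 10 = 10 mL, which is 10/20 = 50% of the present amount.

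**The case against.** The strongest reply is that little depends on this. No primary, secondary or exploratory objective in Section 3 uses stored blood. PD-L1 and *GNAQ/GNA11* status come from tumor tissue, Section 9 specifies no blood-biomarker analysis, and Section 8.2.3 describes the samples as stored for future work. All of that stands, and it sets the priority.

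It might also be said that a separate laboratory manual covers the missing steps. Section 8.2.3 is not redacted and cites no such manual for blood, and the table of contents shows no other blood-processing section. If a manual exists, the protocol should refer to it and agree with it.

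Three stronger readings are tempting, and the documents do not support them:

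- *Planned cfDNA, miRNA and cytokine analyses are lost.* Section 4.2.3.2 lists these only as possibilities. The plan that fails is the isolation of serum.
- *The freezing step contradicts the cytometry plan.* The text shows an omission. The incompatibility is a sound laboratory inference, not something the documents state.
- *A fixed maximum number of draws is lost, namely 29 patients times three.* Enrolment may stop at 10. A progression sample exists only for patients who progress and are sampled. The second-course flow chart in Section 6.2 adds collections at cycles 1 and 2. No single count follows, and any count assumes that sites follow the text literally.

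**Conclusion.** The point holds in a limited form. Section 4.2.3.2 says that serum will be isolated, while Section 8.2.3, supported by footnote 14 and Section 7.1.2.6, stores only a washed cell pellet from heparin tubes. Under literal compliance no draw, however many there are, yields serum or plasma, and no other section repairs this. The conflict and the tube-count slip can be shown from the text alone. The cytometry part rests on the further assumption that the assay needs intact cells.

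The effect is confined to exploratory correlative work. The response-rate analysis, the two-stage rule and the safety reporting do not change. This is a low-priority correction, worth making because the loss cannot be repaired afterwards and the remedy is cheap.

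**What to change.** Within the same 20 mL draw:

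1. **Fluid fraction, preferred option.** In Section 8.2.3, add a step to aliquot and freeze the plasma layer before the washes, and change *serum* to *plasma* in Section 4.2.3.2. The full 20 mL remains available for PBMCs. The receiving laboratory should confirm that heparin plasma suits the assays it may want; the documents do not address this.
2. **Fluid fraction, alternative.** Make one of the two tubes a serum tube and amend footnote 14 to match. This delivers what Section 4.2.3.2 now says, but halves the blood for PBMCs from 20 to 10 mL, a real cost to the cytometry.
3. **Cells.** Freeze PBMC aliquots for cytometry in cryopreservation medium, and keep a dry pellet only for nucleic acid.
4. **Tube count.** Correct three to two in the processing step.

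If serum or cytometry is no longer wanted, delete the corresponding statements, so that Sections 4.2.3.2, 8.1 and 8.2.3 and footnote 14 agree.

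The cost is protocol wording, some cryovials and freezing medium. No extra visit or blood volume is needed.
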